5.2. Number of Participants

The study will screen an estimated 75 potential study participants to ensure randomization of approximately 60 patients with migraine.

5.3. End of Study Definition

End of the study is the date of the last visit or last scheduled procedure shown in the Schedule of Activities (Section 2) for the last patient.

5.4. Scientific Rationale for Study Design

Refer to Section 3.1 for further information.

5.5. Justification for Dose

A galcanezumab 240-mg loading dose (2 consecutive injections of 120 mg each) or a dose of 140 mg erenumab (2 consecutive injections of 70 mg each) will be administered by subcutaneous injection because both galcanezumab and erenumab have been approved in the US at these respective doses for migraine prevention.

6. Study Population

Prospective approval of protocol deviations to recruitment and enrollment criteria, also known as protocol waivers or exemptions, are not permitted.

6.1. Inclusion Criteria

Patients are eligible to be included in the study only if they meet all of the following criteria at screening:

Patient and Disease Characteristics

- [1] Patients are 18 to 55 years of age (inclusive) at the time of screening.
- [2] Have a diagnosis of migraine (1.1 and 1.2 ICHD), with or without aura, as determined by the study investigator and in consideration of International Headache Society International Classification of Headache Disorders – 3rd edition guidelines (ICHD-3 2018).
- [3] Have a frequency of less than 15 monthly headache days of which up to 14 can be migraine headache days.
- [4] Patients can be on no more than 1 other migraine preventive treatment (except for tricyclic antidepressants and verapamil) as long as:
 - that patient has had a stable dose of the oral migraine preventive treatment for a minimum of 2 monthsor
 - patients that have received onabotulinumtoxinA for a minimum of 2 cycles prior to Visit 1.

Informed Consent and Patient Agreements

- [5] Are able and willing to give signed informed consent.
- [6] Are reliable and willing to follow study procedures.
- [7] Male patients must agree to use a reliable method of birth control during the study as well as for 5 months after dosing with study treatment.
- [8] Women of childbearing potential must test negative for pregnancy at the time of enrollment based on a urine pregnancy test.
- [9] Women of childbearing potential who are abstinent from sexual intercourse must agree to remain abstinent during the study as well as for 5 months after dosing with study treatment.

- [10] Otherwise, women of childbearing potential must agree to use 1 highly effective method of contraception (including a male partner who has had a vasectomy), or a combination of 2 effective methods of contraception during the study as well as for 5 months after dosing with study treatment. Birth control is not required if the female is infertile due to surgical sterilization (hysterectomy, or at least 6 weeks after surgical bilateral oophorectomy or tubal ligation) confirmed by medical history or menopause.
- [11] Agree not to post any personal medical data related to the study or information related to the study on any website or social media site (e.g., Facebook, Twitter, LinkedIn, Google+, etc.) until the entire trial has completed.

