WMC administration		X ^a		X		
 • Fasting is defined as no food or drink, except water, for at least 8 hours prior to testing. • No alcohol consumption for 24 hours prior to ingesting the WMC and 6 hours after ingestion. • Tobacco use should also be avoided for 8 hours before ingestion and 6 hours after ingestion of the WMC. • Patients will consume a SmartBar immediately before ingesting WMC and will fast for 6 hours following WMC ingestion. • Patients should not sleep for 6 hours after ingesting the WMC.
Assessment that WMC has been expelled			X ^b	X ^b		The recorder will be returned to the site and data will be uploaded and evaluated to confirm WMC expulsion at Visit 3 and between Visits 4 and 5.
Study treatment administered			X			
Procedures						
Informed consent	X					
Inclusion and exclusion criteria	X					
Concomitant medication review	X	X	X	X	X	

Study Period	SP I Screening and Baseline GI Transit Time		SP II Single-Blind Treatment and Post WMC Evaluation			Notes
	V1	V2	V3	V4	V5	
Urine pregnancy test, performed locally	X				X	
Eligible patient randomized via IWRS			X			
Physical examination	X					
Height	X					
Weight	X					
Medical history	X					
Substance use	X		X	X		Substances: alcohol, caffeine, nicotine, tobacco.
Vital signs	X		X	X	X	Includes body temperature, sitting blood pressure, and pulse.
Assessment of migraine and headache days	X					Will be done retrospectively for the previous month.
GI Symptom Rating Scale (GSRS)	X		X	X	X	
Bristol Stool Form Scale	X		X	X	X	
Spontaneous Bowel movement (SBM) frequency evaluation	X		X	X	X	
Adverse events	X	X	X	X	X	

Abbreviations: GI = gastrointestinal; IBS = irritable bowel syndrome; IWRS = interactive web-response system; SP = study period; TT = transit time; V = visit; WMC = wireless motility capsule.

- ^a If the patient meets the requirement of fasting at Visit 1, then Visit 1 and Visit 2 could be combined. Sites must not instruct patients to fast prior to signing the ICF
- ^b An x-ray may be obtained in the event that the expulsion of the WMC cannot be confirmed.

3. Introduction

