6.2. Exclusion Criteria

Patients will be excluded from study enrollment if they meet any of the following criteria at screening:

Medical Conditions

- [12] Prior to Visit 1, less than 3 bowel movements in the previous 7 days.
- [13] Patients with a history of irritable bowel syndrome (IBS) or chronic constipation.
- [14] Patients with a self-reported history of gastric bezoars, swallowing disorders, severe dysphagia to food or pills, suspected or known strictures, fistulas, or physiological/mechanical GI obstruction.
- [15] History of GI surgery with the exception of cholecystectomy, appendectomy, or Nissen fundoplication.
- [16] History of any abdominal surgery within the past 3 months.
- [17] History of bariatric surgery.
- [18] History of Crohn's disease, celiac disease, ulcerative colitis, or diverticulitis.
- [19] Patients with type 1 or type 2 diabetes.
- [20] Patients with cardiac pacemakers or other implanted or portable electromechanical device.
- [21] Patients with a body mass index (BMI) of ≥ 40 kg/m².
- [22] Women who are pregnant or nursing.
- [23] History of drug or alcohol abuse/dependence within 1 year prior to Visit 1 (excessive or compulsive use as judged by the investigator), or currently using drugs of abuse (including opioids, barbiturates, and marijuana), or any prescribed or over-the-counter medication in a manner that the investigator considers indicative of abuse/dependence.

- [24] Have an acute, serious, or unstable medical condition that, in the judgment of the investigator, indicates a medical problem that would preclude study participation.
- [25] Myocardial infarction, unstable angina, percutaneous coronary intervention, coronary artery bypass graft, stroke, deep vein thrombosis, or pulmonary embolism within 6 months of screening, or have planned cardiovascular surgery or percutaneous coronary angioplasty.
- [26] Patients who, in the clinician's judgment, are actively suicidal and therefore deemed to be at significant risk for suicide, or have had clinically significant suicidal ideation within the past month (e.g., includes some plan or intent to act), or have had any suicidal behavior within the past month.

Prior/Concomitant Therapy

- [27] Patients currently receiving a mAb CGRP antagonist or have received a mAb CGRP antagonist within the past 6 months prior to Visit 1.
- [28] Have received an oral CGRP antagonist (gepant) 14 days prior to Visit 1.

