7.2. Method of Treatment Assignment

Patients who meet all criteria for enrollment will be randomized to single-blind treatment at Visit 3. Assignment to treatment groups will be determined by a computer-generated random sequence using an interactive web-response system (IWRS).

To achieve between-group comparability, the randomization will be stratified by site, BMI category ($<30 \text{ kg/m}^2$, $\geq 30 \text{ kg/m}^2$), and by baseline migraine frequency (<8 migraine headache days versus ≥ 8 migraine headache days).

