7.2.1. Selection and Timing of Doses

The study treatment will be administered only once at Visit 3.

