Appendix 1. Abbreviations and Definitions

Term	Definition
AE	adverse event: Any untoward medical occurrence in a patient or clinical investigation subject administered a pharmaceutical product that does not necessarily have a causal relationship with this treatment. An adverse event can therefore be any unfavorable and unintended sign (including an abnormal laboratory finding), symptom, or disease temporally associated with the use of a medicinal (study) drug, whether or not related to the medicinal (study) drug.
AI	autoinjector
AMY1	amylin 1
ANCOVA	analysis of covariance
blinding/masking	A single-blind study is one in which the investigator and/or staff are aware of the treatment but the patient is not, or vice versa, or when the sponsor is aware of the treatment but the investigator and/or staff and the patient are not.
BSFS	Bristol Stool Form Scale
CGRP	calcitonin gene-related peptide
CIOMS	Council for International Organizations of Medical Sciences
complaint	A complaint is any written, electronic, or oral communication that alleges deficiencies related to the identity, quality, purity, durability, reliability, safety or effectiveness, or performance of a drug or drug delivery system.
compliance	Adherence to all study-related, good clinical practice (GCP), and applicable regulatory requirements.
CRP	clinical research physician: Individual responsible for the medical conduct of the study. Responsibilities of the CRP may be performed by a physician, clinical research scientist, global safety physician, or other medical officer.
CRS	clinical research scientist
CSR	clinical study report
CTT	colonic transit time
eCOA	electronic clinical outcome assessment is a method of capturing data electronically in clinical trials.
eCRF	electronic case report form

Term	Definition
enroll	The act of assigning a patient to a treatment. Patients who are enrolled in the study are those who have been assigned to a treatment.
enter	Patients entered into a study are those who sign the informed consent form directly or through their legally acceptable representatives.
ERB	ethical review board
GCP	Good Clinical Practice
GET	gastric emptying time
GI	gastrointestinal
GSRS	Gastrointestinal Symptom Rating Scale
IB	Investigator's Brochure
ICF	informed consent form
ICH	International Council for Harmonisation

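### No pregnancy test is scheduled at the Visit 3 dosing visit, so the single dose rests on a screening test 6 to 10 days old; adding one is a cheap safety improvement

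*Protocol*

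**What the plan says.** **When the test is done.** In Protocol Section 2, Table CGBC.2.1, the row "Urine pregnancy test, performed locally" is marked at Visit 1 and Visit 5 and is blank at Visits 2, 3 and 4. Section 9.4.2 refers sites back to that table and adds no further test. The row for reviewing inclusion and exclusion criteria is marked at Visit 1 only.

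**When treatment is given.** Section 7.2: "Patients who meet all criteria for enrollment will be randomized to single-blind treatment at Visit 3". Section 7.2.1: "The study treatment will be administered only once at Visit 3".

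**What eligibility requires.** Criterion [8] in Section 6.1: "Women of childbearing potential must test negative for pregnancy at the time of enrollment based on a urine pregnancy test". Criterion [22] in Section 6.2 excludes "Women who are pregnant or nursing". The sentence that opens the list in Section 6.1 reads "Patients are eligible to be included in the study only if they meet all of the following criteria at screening", and the one in Section 6.2 reads "Patients will be excluded from study enrollment if they meet any of the following criteria at screening".

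**What enrolling means.** Appendix 1 defines it as "The act of assigning a patient to a treatment".

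**The concern.** Each drug is given once, by injection, and the dose cannot be taken back. The protocol treats exposure in pregnancy as something to avoid and to follow up. It excludes pregnant women, asks for abstinence or contraception through 5 months after dosing ([9], [10]), withdraws a patient who becomes pregnant (Section 8.2), and collects outcomes for mother and child (Section 9.2.1). Yet a pregnancy that becomes detectable between Visit 1 and Visit 3 would not be looked for until Visit 5, after the exposure.

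There is also a smaller drafting problem. With the Appendix 1 definition, criterion [8] points to a test at treatment assignment, which is Visit 3. The schedule contains no such test.

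**Working it through.** The documents give no figure for the age of the test at dosing, so there is none to reproduce. The visit windows in Table CGBC.2.1 supply it.

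**1. Age of the test at dosing**
- Visit 1 is Day -8 ± 2, that is Day -10 to Day -6. Visit 3 is Day 0.
- Age = 0 - (Visit 1 day) = 6 to 10 days, nominally 8.
- Footnote a lets Visits 1 and 2 be combined. Visit 2 is Day -7 ± 2, that is Day -9 to Day -5. A combined visit inside both windows falls on Day -9 to Day -6, giving 6 to 9 days. If it is dated by the Visit 2 window alone, the range is 5 to 9 days. Five days is therefore the extreme lower value.
- Cross-check: Table CGBC.7.1 labels the dose Day 7 ± 2. Read as days from Visit 2, with Visit 1 nominally one day earlier, this gives 7 + 1 = 8 days, the same nominal age.

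**2. Time to the next test**
- Visit 5 is Day 28 ± 3, so the next scheduled test is 28 - 3 = 25 to 28 + 3 = 31 days after the dose.

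**3. What a Visit 3 test would add**
- Assumption, not in the documents: a urine test turns positive L = 10 to 21 days after conception.
- Conceptions that can be missed at dosing now: gap + L, from 6 + 10 = 16 to 10 + 21 = 31 days before the dose (5 + 10 = 15 at the combined-visit extreme).
- With a Visit 3 test: L alone, 10 to 21 days. The blind period shrinks by the length of the gap and does not vanish.
- On the same assumption, a pregnancy newly detectable by Visit 3 was conceived at least 10 days before Visit 3. The gap is at most 10 days, so conception was at or before Visit 1. A Visit 3 test would therefore catch pregnancies already under way when the study agreements in [9] and [10] began.

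**4. How often this could matter**
- Step 3 means that a pregnancy rate under the study's contraception rules is the wrong rate, and the documents give no other. No estimate is offered, only a break-even.
- Suppose all 60 randomized patients were women of childbearing potential with the longest gap: 60 × 10 / 365 = 1.64 woman-years.
- An expected count of 1 would then need 1 / 1.64 = 0.61 such pregnancies per woman-year. The real count is likely well below 1.

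**5. What criterion [8] requires**

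| Points to Visit 3 | Points to Visit 1 |
|---|---|
| Appendix 1 equates enrolling with treatment assignment | The opening sentences of 6.1 and 6.2 both set the time as screening |
| Section 7.2 places assignment at Visit 3 | Table CGBC.2.1 marks eligibility review at Visit 1 only |
| | Section 5.1 gives the Visit 2 capsule to patients who already qualify in full |
| | Section 9.1.1 uses the word enrolled for the step before swallowing the capsule |

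The defined term points one way and most of the operational text points the other.

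**The case against.** The strongest defence is that the plan is workable and already layered. A site that follows the table knows when to test. No passage expressly calls for a test on the day of dosing. Both products are given at doses approved in the US, and the documents give no fetal-risk figure for either. Women must test negative at Visit 1 and agree to abstinence or contraception. Pregnancy leads to discontinuation and outcome reporting, Visit 5 has a test, and SAP Appendix 1 lists a positive pregnancy test as an important eligibility deviation.

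Much of this stands. It keeps the wording conflict minor and the point optional. It does not close the gap, because none of these measures detects a pregnancy between Visit 1 and the injection. The contraception agreements help least here: on the assumed lag, the pregnancies a Visit 3 test would newly find predate them.

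A reader might infer that every woman randomized under this schedule breaches criterion [8]. The documents do not support that. It follows only if the Appendix 1 definition overrides the opening sentence of Section 6.1, the eligibility row and Sections 5.1 and 9.1.1, and screening is the likelier intent.

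**Conclusion.** The point holds as a low-frequency patient-safety improvement. The single, irreversible dose is given on a pregnancy test 6 to 10 days old (5 at the extreme), and the next test is 25 to 31 days later. These intervals rest only on the visit windows in Table CGBC.2.1. The ambiguity in [8] is real but secondary.

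Two further inferences should be resisted. One is a forecast of exposed pregnancies: the documents give neither the share of women of childbearing potential nor a rate for conceptions before Visit 1, so the most that can be said is that the expected number is likely well below 1. The other is that a Visit 3 test would rule out exposure. It shortens the undetectable period, does not remove it, and does nothing about conceptions after the dose. No statistical result changes.

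**What to change.** - In Table CGBC.2.1, mark the local urine pregnancy test at Visit 3, with a note that a negative result is needed before the IWRS randomization and before dosing.
- Reword the timing in criterion [8] to: *at screening (Visit 1) and before randomization at Visit 3*. This also removes the conflict with Appendix 1.

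The cost is one extra local urine test per woman of childbearing potential, so no more than about 60 tests even if every randomized patient were in that group, plus the amendment wording. The test is already in use in the study and the visit already exists. Done early in the visit, it would also inform any x-ray that footnote b allows when capsule expulsion is unconfirmed. Sample size, power and the primary analysis are unaffected.

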6.2. Exclusion Criteria

Patients will be excluded from study enrollment if they meet any of the following criteria at screening:

Medical Conditions

- [12] Prior to Visit 1, less than 3 bowel movements in the previous 7 days.
- [13] Patients with a history of irritable bowel syndrome (IBS) or chronic constipation.
- [14] Patients with a self-reported history of gastric bezoars, swallowing disorders, severe dysphagia to food or pills, suspected or known strictures, fistulas, or physiological/mechanical GI obstruction.
- [15] History of GI surgery with the exception of cholecystectomy, appendectomy, or Nissen fundoplication.
- [16] History of any abdominal surgery within the past 3 months.
- [17] History of bariatric surgery.
- [18] History of Crohn's disease, celiac disease, ulcerative colitis, or diverticulitis.
- [19] Patients with type 1 or type 2 diabetes.
- [20] Patients with cardiac pacemakers or other implanted or portable electromechanical device.
- [21] Patients with a body mass index (BMI) of ≥ 40 kg/m².
- [22] Women who are pregnant or nursing.
- [23] History of drug or alcohol abuse/dependence within 1 year prior to Visit 1 (excessive or compulsive use as judged by the investigator), or currently using drugs of abuse (including opioids, barbiturates, and marijuana), or any prescribed or over-the-counter medication in a manner that the investigator considers indicative of abuse/dependence.

- [24] Have an acute, serious, or unstable medical condition that, in the judgment of the investigator, indicates a medical problem that would preclude study participation.
- [25] Myocardial infarction, unstable angina, percutaneous coronary intervention, coronary artery bypass graft, stroke, deep vein thrombosis, or pulmonary embolism within 6 months of screening, or have planned cardiovascular surgery or percutaneous coronary angioplasty.
- [26] Patients who, in the clinician's judgment, are actively suicidal and therefore deemed to be at significant risk for suicide, or have had clinically significant suicidal ideation within the past month (e.g., includes some plan or intent to act), or have had any suicidal behavior within the past month.

Prior/Concomitant Therapy

- [27] Patients currently receiving a mAb CGRP antagonist or have received a mAb CGRP antagonist within the past 6 months prior to Visit 1.
- [28] Have received an oral CGRP antagonist (gepant) 14 days prior to Visit 1.
- [29] Known hypersensitivity to monoclonal antibodies or other therapeutic proteins, or to galcanezumab.
- [30] Known allergy to SmartBar ingredients including granola (rolled oats, evaporated cane juice, expeller pressed canola oil, defatted wheat germ, oat flour, brown rice syrup, molasses, salt, natural flavor, soy lecithin), whey crisp, rice syrup, corn syrup, whey protein isolate, invert sugar, puffed wheat, apples, maltodextrin, sorbitol, apple juice concentrate, partially hydrogenated vegetable oil (cottonseed, soybean), honey, natural and artificial flavor, salt, gluten, vanilla.
- [31] Medications known to alter GI transit times including opioids, tricyclic antidepressants, verapamil, and medications that can affect the WMC test such as proton pump inhibitors, are excluded from the study 1 week prior to Visit 2 and at any time after Visit 2. See medication exclusion list for a full list of excluded medications.

Prior/Concurrent Clinical Trial Experience

- [32] Are currently enrolled in any other clinical study involving an investigational product or any other type of medical research judged not to be scientifically or medically compatible with this study.

Other Exclusions

- [33] In the opinion of the investigator, have other issues that would interfere with compliance with the study requirements and completion of evaluations required for this study.

- [34] Are investigator site personnel directly affiliated with this study and/or their immediate families. Immediate family is defined as a spouse, parent, child, or sibling, whether biological or legally adopted.
- [35] Are Lilly employees or are employees of Medtronic.
- [36] Are unwilling or unable to comply with the use of a data collection device to directly record data from the subject.

6.3. Lifestyle Restrictions

No vigorous exercise, such as sit-ups, abdominal crunches, or prolonged extreme exercises, should be performed throughout the duration of the WMC test, which is approximately 5 days.

Patients should maintain consistent dietary habits throughout the duration of the study (from Visit 1 to Visit 5).

6.4. Screen Failures

Individuals who do not meet the criteria for participation in this study (screen failure) may be considered for rescreen once, with approval from Lilly Medical for only the criteria shown below. The interval between screening and rescreening must be at least 45 days or longer if required for the specified time frames in the inclusion/exclusion criteria or concomitant medication list. If rescreening is performed, the individual must sign a new ICF and will be assigned a new identification number.

- Inclusion criterion 1: If patients are less than 18 years old at the time of informed consent, they may be rescreened when they reach 18 years of age during the study enrollment period.
- Exclusion criterion 27, 28, and 31: Patients using a concomitant medication that requires a stable dose for a specific duration prior to Visit 1 may be rescreened if additional time is needed to meet the duration requirement.

7. Treatments

